## **2. Objectives of the study**

The study intends to recruit a group of people who have undergone appendectomy for colonoscopy, (1) to observe changes in gut microbiota before and after colonoscopy in the appendectomy population; (2) To analyze whether the changes in gut microbiota before and after colonoscopy in the appendectomy population were different from the recovery of the normal population.

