### **Iii. Study Design**

This study uses a parallel controlled monitoring clinical trial approach to investigate the short-term and long-term effects of PEG use on the gut microbiota of patients, including tracking analysis of the recovery and impairment of the gut microbiota, and comparing the recovery and impairment of the microbiota with those who did not undergo appendectomy to design corresponding microecological restoration probiotics. This study used bioinformatics methods to statistically analyze the data information of the samples.

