## 5. Estimation of sample size

About 10 people were included in this study.

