Additionally, calculate the Bray-Curtis distance using the vegan package for principal coordinate analysis (PCoA). Linear discriminant analysis effect size (LEfSe) analysis was used for the Kruskal-Wallis test and the Wilcoxon rank sum test, and a  $p < 0.05$  was considered statistically significant. The LDA score was set to 2.0 to identify the characteristics with significant differences between groups. This study retained taxa with an average relative abundance greater than 0.0001(0.01%). The bar charts were visualized using the "ggplot2" package in R software (version 4.0.5)(<https://www.r-project.org/>).

All data were expressed as mean  $\pm$  standard error (SEM). The differences between groups were analyzed by one-way ANOVA using GraphPad Prism 7.0 software, and the results of the analysis were obtained by Tukey Test.

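### The objectives concern within-person change and its difference between populations, but every test the protocol names is for independent samples and none has a person-level term

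*Protocol*

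**What the plan says.** Protocol Section 2 (Objectives) sets two aims. The first is "to observe changes in gut microbiota before and after colonoscopy in the appendectomy population", a comparison of each person with himself or herself. The second asks whether those changes "were different from the recovery of the normal population", which is a between-group difference in change. Section III (Study Design) confirms follow-up over time, "including tracking analysis of the recovery and impairment of the gut microbiota", covering short- and long-term effects. Section 5 gives the size: "About 10 people were included in this study".

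Section VIII (Data collection and statistical analysis) fixes the tests. LEfSe "was used for the Kruskal-Wallis test and the Wilcoxon rank sum test", with significance at p < 0.05. For the remaining data, "The differences between groups were analyzed by one-way ANOVA using GraphPad Prism 7.0 software", and "the results of the analysis were obtained by Tukey Test". Results are to be shown as mean ± SEM. Bray-Curtis distances are used for an ordination, with no test attached. The section names no paired test, repeated-measures or mixed model, subject term, change score or group-by-time term, and it does not define what a group is.

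**The concern.** One-way ANOVA, Tukey, Kruskal-Wallis and the rank sum test all treat each sample as coming from a different person. In a study that samples the same people repeatedly, this fits the objectives only if the tests are confined to comparisons between different people.

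With about 10 participants, the main strength of the design is that each person serves as his or her own control. A test that ignores the person leaves between-person variation in the error term, so a real effect of bowel preparation could be missed. The second objective needs a contrast of changes, and none of the named tests provides one as specified. An SEM at each visit likewise shows spread between people, not the uncertainty of the change.

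A protocol may leave detail to a statistical analysis plan. Here, however, the protocol names the tests and the software, so the issue is a method fixed in a form that does not match the objectives.

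**Working it through.** The protocol gives no power, effect-size or variance figure, so there is no stated number to reproduce.

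**Inputs from the protocol.** Two objectives (Section 2), tracking over time (Section III), about 10 people (Section 5), independent-samples tests and p < 0.05 (Section VIII).

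**Assumptions not in the protocol.** 5 people per group; 2 or 4 visits (the text gives no count, and the study-process figure is not shown); normal outcome with SD 1; equal within-person correlation ρ of 0.5–0.8; two-sided tests. Simulations used 20,000 runs per setting.

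**Step 1: what each meaning of 'group' implies.**

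| Groups are | Consequence |
|---|---|
| Visits | Same people in each group; pairing ignored |
| Population-by-visit cells | Person ignored; omnibus type I error stays near nominal (about 4–7%), but neither it nor a Tukey pair tests the difference in change |
| Two populations, visits pooled | Repeat samples counted as extra people |
| Populations at one visit | Valid, but objective 1 and the difference in change are left without a test |

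**Step 2: before/after, pairing ignored.** The variance used is 2σ²/n; the true variance is 2σ²(1−ρ)/n. The standard error is therefore too large by 1/√(1−ρ):
- ρ = 0.5: 1/√0.5 = 1.41
- ρ = 0.7: 1/√0.3 = 1.83
- ρ = 0.8: 1/√0.2 = 2.24

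Simulated type I error of the one-way test on two visits with 5 people is 1.5% at ρ = 0.5, about 0.6% at 0.7 and about 0.3% at 0.8, against 5% nominal. At ρ = 0 it is 5%.

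**Step 3: power with equal adjustment.** Take a 1.5 SD change in one group and Bonferroni over the post-versus-baseline contrasts in both groups: 2 × (2−1) = 2 contrasts with 2 visits, 2 × (4−1) = 6 with 4 visits.

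| Visits | Person ignored | Subject-adjusted model |
|---|---|---|
| 2 | 48–49% | 72–99% |
| 4 | 31–32% | 69–99% |

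The ranges run over ρ = 0.5–0.8. At ρ = 0 pairing brings no gain. For example, with 5 people and an unadjusted test of a 1 SD shift, power is 29% unpaired and 23% paired.

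**Step 4: populations compared with visits pooled (conditional).** With T visits the true variance of a group mean exceeds the assumed one by 1 + (T−1)ρ:
- T = 2: 1.5 to 1.8, so the standard error is too small by √1.5 = 1.22 to √1.8 = 1.34
- T = 4: 2.5 to 3.4, so it is too small by √2.5 = 1.58 to √3.4 = 1.84

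Simulated type I error is about 12–17% with 2 visits and 23–32% with 4. At ρ = 0 it is about 5%.

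**The case against.** The strongest reply is that Section VIII refers only to differences between groups. It never says that before/after samples are tested this way or that visits are pooled. For the two populations at a single visit, the named tests are correct. This stands, but on that reading nothing in the protocol tests the within-person change or the difference in change.

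A reader might infer from the Tukey step that the groups must be visits or cells, since only two populations exist. That is plausible but not proven. Section 4 gives two routes into the appendectomy arm, one of them linked to right-sided colon cancer. With controls, three groups of different people is a possible reading.

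A reader might also infer that the plan inflates false positives. That requires pooled visits, which no section describes. Under the cell reading, a group comparison at the same visit rejects a true null 5.4–6.5% of the time unadjusted and 0.4–1.6% with Tukey.

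Finally, setting Tukey over all cell pairs against a single unadjusted paired contrast would overstate the cost of ignoring pairing. At ρ = 0.5 with 2 visits, power is 32% with Tukey, 64% unpaired without adjustment and 84% with an unadjusted mixed model. Most of that gap is multiplicity adjustment: 64 − 32 = 32 of 84 − 32 = 52 points. For this reason the comparison in the working uses equal adjustment.

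The study is also small and observational in tone, with no stated primary endpoint or power claim, and on the before/after reading the error is conservative. These points lower the severity but do not remove the mismatch.

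**Conclusion.** The concern holds: on every reading of 'group', the named tests either ignore the person or leave the study's two questions without a suitable test. If the tests are used across visits, the before/after analysis is too conservative (type I error about 0.3–1.5%) and loses substantial power at the correlations assumed. The documents do not support saying that the plan will produce false positives; that holds only if visits are pooled.

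The directions of error follow from the formulas for any positive ρ. The sizes rest on the assumed correlation, group split, visit count and effect size, none of which the protocol gives. This should be fixed, but the text does not show that the results will be invalid.

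**What to change.** In Section VIII, define what a group is and replace one-way ANOVA with Tukey by a mixed model for a summary outcome such as a diversity index, suitably transformed. Include group, visit, group × visit and a random intercept for subject. Test two sets of planned contrasts, with multiplicity adjustment over these only:

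- Objective 1: each post-colonoscopy visit against own baseline within the appendectomy group.
- Objective 2: the group × visit contrast, that is, the between-group difference in change from baseline. Testing each group's change separately would not answer this objective.

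For taxa, use a person-level paired or mixed model for before/after comparisons in place of the unpaired LEfSe tests. Keep independent-samples tests for comparing populations at one visit or comparing person-level changes. A signed-rank test on 5 pairs is not a useful substitute: its smallest two-sided p-value is 2/2⁵ = 0.0625. Report the mean within-person change with a 95% confidence interval.

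The cost is a rewording of Section VIII and a few lines of R, which the plan already uses; no extra samples or visits are needed. The downside is reliance on normality on the transformed scale and equal correlation across visits, which about 10 people can barely check. Objective 2 will also remain imprecise: with equal group sizes and equal variances, the difference between two independent changes has a standard error √2 = 1.41 times that of one group's change.

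### If the ANOVA groups are group-by-visit cells, Tukey corrects for all cell pairs while none tests the difference in change; a short planned list fits the objectives better

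*Protocol*

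**What the plan says.** The protocol's section on data collection and statistical analysis (VIII) states "The differences between groups were analyzed by one-way ANOVA using GraphPad Prism 7.0 software", and continues "and the results of the analysis were obtained by Tukey Test". It does not say which groups enter, whether visits form part of them, or whether the response is the value at a visit or each person's change. The 0.05 level appears in the sentence on LEfSe.

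The objectives section asks two questions. The first is "to observe changes in gut microbiota before and after colonoscopy in the appendectomy population". The second is "To analyze whether the changes in gut microbiota before and after colonoscopy in the appendectomy population were different from the recovery of the normal population". The sample size section says "About 10 people were included in this study", without a split between appendectomy and control subjects. The number of sampling visits is not in the readable text. The study process section refers to a technical route that is not shown here, so its absence is not held against the plan.

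**The concern.** The design names two populations. With two groups at one visit, Tukey's procedure is the ordinary t-test, so naming it changes nothing. It has an effect only if more than two groups enter. One natural way for that to happen is for each group at each visit to be a separate cell.

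On that reading two things go wrong. Tukey protects every pair of cells, including one group before colonoscopy against the other group afterwards, a comparison that neither objective asks for. And the second objective is a difference of two changes, a contrast over four cells, which no pairwise test addresses. The plan would pay for a wide family of comparisons and still leave out the one that answers its second question. With roughly five people per cell, the critical value has a large influence on what can be detected.

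**Working it through.** The protocol gives no power, effect size or standard deviation, so there is no figure of its own to reproduce.

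**Inputs**
- From the protocol: about 10 people; level 0.05; one-way ANOVA with Tukey.
- Assumed: 5 per group, two-sided tests, groups = group-by-visit cells, k = 2 to 5 visits, independent cells, true difference between two cells d = 2 SD.

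**Check with two groups only.** On 8 degrees of freedom, q(0.95; 2, 8)/√2 = 2.306 and t(0.975; 8) = 2.306. They are identical, so the loss is zero.

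**Pairs.** There are 2k cells and 2k(2k−1)/2 pairs. Of these, k are same-visit pairs, k(k−1) are within-group pairs, and the rest cross both group and visit. For k = 2: 6 − 2 − 2 = 2.

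**Formulas**
- Error degrees of freedom: 2k × (5−1) = 8k.
- Tukey critical t: q(0.95; 2k, 8k)/√2.
- Planned list: k−1 group differences in change plus k−1 changes in the appendectomy group, so 2(k−1) contrasts. Bonferroni critical t: t(1 − 0.025/[2(k−1)]; 8k). Holm never rejects fewer hypotheses than this.
- Power of a two-cell contrast: non-central t with 8k degrees of freedom and non-centrality 2/√(2/5) = 3.162.

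| Visits k | All pairs | Cross pairs | Planned contrasts | Critical t: Tukey | Critical t: planned list | Critical t: one uncorrected | Power: Tukey | Power: planned list | Power: one uncorrected |
|---|---|---|---|---|---|---|---|---|---|
| 2 | 6 | 2 | 2 | 2.86 | 2.47 | 2.12 | 62% | 75% | 84% |
| 3 | 15 | 6 | 4 | 3.09 | 2.70 | 2.06 | 54% | 68% | 86% |
| 4 | 28 | 12 | 6 | 3.24 | 2.81 | 2.04 | 48% | 64% | 87% |
| 5 | 45 | 20 | 8 | 3.35 | 2.89 | 2.02 | 44% | 61% | 87% |

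The planned list gains 75 − 62 = 13 points with two visits and 61 − 44 = 17 with five. Against one uncorrected contrast the gap is 84 − 62 = 22 to 87 − 44 = 43 points.

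**How much is due to the cross pairs alone.** Drop only the pairs that differ in both group and visit, and keep correcting for the rest. With simulated critical values (2.72 against Tukey's 2.86 for two visits), at most 4.8 to 5.8 points come back for 2 to 4 visits, whatever the effect size. With Bonferroni over the remaining 4, 9, 16 or 25 pairs, power at 2 SD is 64%, 55%, 50% and 45%, about 2 points above Tukey.

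**The difference in change.** This contrast has four cells. With independent cells its non-centrality for a 2-SD difference in change is 2/√(4/5) = 2.236. Bonferroni over the same list then gives power of 43%, 34%, 30% and 27% for 2 to 5 visits. Within-person correlation raises this. In a simulation with two visits, 5 per group and no multiplicity correction, power for a 2-SD difference in change was 50%, 65%, 79% and 95% at correlations of 0, 0.3, 0.5 and 0.7.

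**The case against.** The strongest objection is that the protocol never describes group-by-visit cells. The ANOVA could compare the two populations only, where Tukey is harmless; if the response were each person's change, that comparison would even address the second objective. It could also compare visits within one group, where no pair crosses groups. The choice of contrasts is often left to a statistical analysis plan, and none is shown. This stands: the point is conditional.

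A reader might infer that the comparisons nobody asked for cost 20 to 40 points of power. The documents do not support that. The cross pairs account for at most about 5 to 6 points. The larger range appears only against a single uncorrected contrast, which is not what is proposed here. Most pairs in the family (4 of 6 with two visits, 25 of 45 with five) are same-visit or within-group comparisons, so the protection is not all wasted.

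A reader might also infer that the planned list raises power for the second objective. It does not under independent cells: 43% to 27% for the difference in change is below Tukey's 62% to 44% for a two-cell difference. These are different quantities, and Tukey does not test the former at all.

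Finally, Tukey is a valid and conservative procedure, and the study is small with no stated power target. One-way ANOVA on repeated samples from the same people is a larger weakness than the multiplicity method, so replacing Tukey alone would not repair the analysis. That also stands, and it is why the fix works on each person's own change.

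**Conclusion.** The point holds conditionally and is minor. What the protocol fixes is one-way ANOVA with Tukey as the source of its results. What it asks is a change within one group and whether that change differs between groups. If the groups are group-by-visit cells, the family is wider than the objectives need and leaves out the second objective.

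For a two-cell contrast of 2 SD, a planned list with family-wise control gains about 13 to 17 points of power over Tukey. That size rests on 5 people per cell, independent cells, and 2 to 5 visits, none of which the readable text states. If only the two populations are compared at one visit, the power cost is nil.

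**What to change.** In section VIII, replace the Tukey test with contrasts named in advance and computed on each person's change from their own baseline:

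- (a) the difference in change between appendectomy and control subjects at each post-colonoscopy visit;
- (b) the change from baseline in the appendectomy group at each of those visits.

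Apply Holm adjustment over this list, and state the number of visits that enter it. For (a), the reason for the change is that the stated objective is then tested; its power depends on the within-person correlation, so the text should claim no gain.

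The cost is a few sentences, with no added participants or samples. The downside is that all other cell pairs become descriptive and can no longer be called significant.
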